13. LFTs – albumin, total bilirubin, direct bilirubin, indirect bilirubin, alkaline phosphatase (ALP), aspartate aminotransferase (AST), alanine aminotransferase (ALT), total protein, gamma-glutamyl transferase (GGT), and lactate dehydrogenase (LDH);

Immunology - CPT™ for PBMC by ELISPOT and PAXgene for RNA. PAXgene samples will be stored for analysis at the end of study.

14. Hepatic transaminases and FIX transgene expression will be monitored twice-weekly or thrice-weekly to detect early changes. Between Weeks 1 and 12 post-vector infusion, monitoring will include LFTs, FIX:C, FIX Ag, CPT™ for PBMC by ELISPOT and PAXgene for RNA. Spare plasma, from already collected blood samples will be stored for repeat or additional tests. Some participants may need more frequent monitoring using unscheduled visits.
15. Activated partial thromboplastin time (aPTT) measured in seconds; TAT will be taken just prior to the infusion of FIX product.
16. Participants should be advised to temporarily suspend prophylaxis regimen after vector infusion until being advised by the Investigator to resume.
17. At Day 0, participants should arrive at the clinic with at least 96 hours (4 days) washout of pd-FIX/rFIX or up to 168 hours (7 days) washout of extended half-life FIX product. Participants will receive a single IV infusion of 100 IU/kg of FIX protein product over 10 (±2) minutes.
18. Blood samples will be collected at pre-infusion, 10 (±2) minutes, 1 hour ± 10 minutes, 3 hours ± 10 minutes, 6 hours ± 10 minutes, and 24 (±1) hours from the start-of-infusion of FIX protein product.
19. Thromboelastography (TEG) and/or rotational thromboelastogram (ROTEM) – Only selected participants at selected sites capable of performing these tests locally.  
CCI  
Blood samples will be collected at pre-infusion and 10 (±2) minutes from the start-of-infusion of FIX protein product on Day 0 and End-of-Study Visits.
20. After the completion of FIX protein product infusion, participants will receive PF-06838435 infused via infusion pump over a period of approximately 60 minutes.
21. Haem-A-QoL, EQ-5D-5L, McGill pain questionnaire, and Hemophilia Activities List (including Changes in Level of Activity) questionnaires will be completed by the participants.  
CCI  
[REDACTED]
23. Immunomodulation See [Appendix 2](#): possible tests below:  
LFT – albumin, total bilirubin, direct bilirubin, indirect bilirubin, ALP, AST, ALT, total protein, GGT, and LDH;  
Coagulation –aPTT, FIX:C, FIX Ag  

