#### **4.1.7.2. Dosing Day**

Assessments and procedures to be performed on Dosing Day (Day 0) are described in the Schedule of Activities. Participants will receive a bolus infusion of FIX protein product in about 10 minutes for FIX incremental recovery ([Section 6.1.1](#)) followed by a single IV infusion of PF-06838435 at the vector-administration center. The complete dose of PF-06838435 will be infused via infusion pump over a period of approximately 60 minutes under medical supervision. Vital signs will be taken at various time-points up to approximately 24 hours from the start of infusion (see Schedule of Activities).

Blood samples for FIX incremental recovery will be collected pre-infusion of the FIX protein product, 10 ( $\pm 2$ ) minutes [end-of-infusion], 1 hour  $\pm 10$  minutes, 3 hours  $\pm 10$  minutes, 6 hours  $\pm 10$  minutes, and 24 ( $\pm 1$ ) hours from the start-of-infusion. Samples for thrombin generation assessments will also be collected pre-infusion and 10 ( $\pm 2$ ) minutes from the start-of-infusion of FIX protein infusion and evaluated by an CCI performed at the central laboratory. For participants at selected sites, depending on the testing capabilities, additional samples for global hemostasis such as whole blood TEG and/or ROTEM may also be collected pre-infusion and 10 ( $\pm 2$ ) minutes from the start-of-infusion of FIX protein infusion and evaluated locally.

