### 6.1.2. FIX Incremental Recovery of FIX Products

Participants should be reminded to have washout of at least 96 hours (4 days) without FIX protein product, or longer washout for extended half-life FIX protein product, prior to any blood draw and infusion on Day 0. On Day 0 participants will be infused with 100 IU/kg of their usual FIX protein product over 10 (±2) minutes, under the supervision from the site staff and/or Investigator(s) to assess FIX incremental recovery. Number of vials, total volume, and total dosage are monitored and recorded by the site staff.

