4.3.5. FIX Incremental Recovery Analysis Set

The FIX incremental recovery analysis set will include subjects who have received 100 IU/kg of FIX protein product infusion and have completed a blood sample collection

within the first 3-hours post infusion for FIX protein product enabling determination of FIX incremental recovery. The FIX incremental recovery analysis set will be used for the summary of FIX incremental recovery described in Section 10.1.

5. Subject Disposition

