10.1. FIX Incremental Recovery

The FIX incremental recovery analysis will be using subjects in FIX incremental recovery analysis set. Blood samples for FIX activity will be collected pre-infusion of the FIX protein product and at least one sample within 3-hours post infusion. FIX activity -time

data along with the FIX antigen data will be presented in listings and summarized by dose group in a table.

Incremental recovery is determined as the peak factor level recorded within 3-hours after infusion and is reported as [IU/ml]/[IU/kg] using the following formula:

$$[(\text{Activity IU/mL peak post infusion}) - (\text{Activity IU/mL pre-infusion})] / (\text{IU/kg infused})$$

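### The first incremental-recovery sample shares the 8 to 12 minute window of the FIX infusion itself, so an in-window draw can come before the dose is complete

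*Protocol*

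**What the plan says.** Schedule of Activities (SoA) note 17 gives the dose and duration: "Participants will receive a single IV infusion of 100 IU/kg of FIX protein product over 10 (±2) minutes". Protocol 6.1.2 repeats it: "100 IU/kg of their usual FIX protein product over 10 (±2) minutes".

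SoA note 18 gives the sampling times: "Blood samples will be collected at pre-infusion, 10 (±2) minutes, 1 hour ± 10 minutes, 3 hours ± 10 minutes", then 6 hours, and finally "24 (±1) hours from the start-of-infusion of FIX protein product". All times therefore run from the start of the FIX product infusion. Protocol 4.1.4 gives the same schedule. Protocol 4.1.7.2 also counts from the start, but adds a label to the 10-minute draw: "minutes [end-of-infusion], 1 hour". The label does not appear in note 18 or in 4.1.4.

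Thrombin-generation samples (4.1.4, 4.1.7.2) and TEG/ROTEM samples (the same sections and note 19) are taken pre-infusion and at the same 10 (±2) minutes.

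SAP 10.1 sets the numerator: "Incremental recovery is determined as the peak factor level recorded within 3-hours after infusion". It subtracts the pre-infusion level and divides by the IU/kg infused. It asks for "at least one sample within 3-hours post infusion", and SAP 4.3.5 defines the analysis set by a sample "within the first 3-hours post infusion for FIX protein product enabling determination of FIX incremental recovery". Protocol 9.3 defines the same set by a sample 30 (±2) minutes after infusion, which is not on the schedule.

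**The concern.** The 10-minute draw is the one meant to catch the peak, and the next is about 50 minutes later. If it is taken while product is still running in, the level reflects part of the dose while the formula divides by all of it. If an analyst decides that such a draw is not after infusion, the peak falls back to the 1-hour sample. SAP 10.1 does not say which applies. Any error is in one direction for recovery, and Tmax can shift for a reason unrelated to the product.

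Tmax and percent recovery are listed among the endpoints for the primary objective (Protocol 1.1 and 3; incremental recovery also in SAP 3.2.1). The thrombin-generation and TEG/ROTEM draws have no later Day 0 sample to compensate, so an early draw there is simply a partial-dose result.

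**Working it through.** The documents state no recovery value and no test or power figure for it, so there is nothing to reproduce. The check is of the timing and of what the SAP's peak rule does with it. All percentages refer to the rise above the pre-infusion level.

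**Inputs from the documents.** Infusion duration D is 8 to 12 minutes (note 17, 6.1.2). First draw s is 8 to 12 minutes from the start (note 18, 4.1.4). The next draw is at 1 hour ± 10 minutes. The numerator is the peak within 3 hours and the denominator is the dose infused (SAP 10.1).

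**Assumptions.** Constant infusion rate. The fall from end of infusion to 1 hour is not in the documents and is shown as a range. For averages only, s and D are independent and uniform on 8 to 12 minutes.

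**Step 1: share of the dose delivered at the first draw.** f = min(1, s/D).
- s = 8, D = 12: 8/12 = 66.7%
- s = 8, D = 10: 8/10 = 80.0%
- s = 10, D = 12: 10/12 = 83.3%
- s at or after D: 100%

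Under the uniform assumption half of the draws are early. The mean of f is 87.8% among those and 0.5 × 100% + 0.5 × 87.8% = 93.9% overall.

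**Step 2: apply the SAP peak rule, counting the early draw.** The recorded peak relative to the end-of-infusion value is max(f, 1 − fall).

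| Assumed fall to 1 h | Worst-case understatement | Mean understatement | 1-hour sample is the peak |
|---|---|---|---|
| 3% | 3% | 1.4% | 43% |
| 10% | 10% | 3.8% | 27% |
| 20% | 20% | 5.6% | 10% |

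The last column is the share of participants whose Tmax moves to about 1 hour on this reading.

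**Step 3: if early draws are not counted.** Each early draw then loses the whole fall. With half early, the mean is 0.5 × 3% = 1.5%, 0.5 × 10% = 5% and 0.5 × 20% = 10%. The worst case is still the fall itself, and every early draw moves Tmax to about 1 hour.

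**Step 4: a model-based size for the fall.** With one compartment, the 1-hour value relative to the end-of-infusion value is exp(−ln 2 × (60 − D)/half-life in minutes). For D = 12, s = 8 and assumed half-lives of 10, 18, 24 and 80 hours, this gives 94.6%, 97.0%, 97.7% and 99.3%. The worst-case understatement is then 5.4% down to 0.7%. A larger fall through distribution would raise it.

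**Step 5: the extreme.** If the early draw is counted and no other sample exists within 3 hours, the shortfall is 1 − f, at most 1 − 8/12 = 33.3%.

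**The case against.** The strongest reply is that the intent is plain. Section 4.1.7.2 calls this the end-of-infusion sample, and site staff would naturally draw when the infusion stops, so the two tolerances move together. That is a fair reading, and a site that works this way has no error. It does not settle the matter: the same sentence in 4.1.7.2 still counts from the start of infusion, and a site following the SoA notes or 4.1.4 sees no such label.

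A second reply is that the SAP already covers it, because its peak is limited to levels after infusion. Read literally, that excludes an early draw, but the peak then comes from the 1-hour sample, so the error is bounded rather than removed.

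A third reply is that little depends on it. The analysis is descriptive, recovery measures the participant's own FIX product on Day 0 and not vector-derived activity, and the visible escalation and expansion rules do not use it. TEG/ROTEM is done only at selected sites, and neither it nor thrombin generation is shown with a dose-normalised formula. All of this stands and keeps the point minor.

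A reader might infer that recovery will generally be understated, or that half of all draws will be early. The documents support neither. At nominal times the draw falls at the end of infusion, and draws at or after completion lose nothing. The one-half follows from assuming two independent times with the same distribution; it would appear for any window width and says nothing about site practice.

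**Conclusion.** The point holds as a timing gap: the stated windows allow the first post-dose draw up to 4 minutes before the dose is complete, and no rule in either document deals with such a draw. When it occurs, recovery can be understated and Tmax can move to about 1 hour.

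The size is modest. With the scheduled 1-hour sample present, the recovery error cannot exceed the fall from end of infusion to 1 hour. That fall is an assumption here, as are the constant rate and, for the averages, the independent uniform windows.

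A reader might take the 33% shortfall in dose delivered as the error in the endpoint. It is not, because SAP 10.1 does not rest on the 10-minute value alone. That figure is reached only when the early draw is counted and stands alone within 3 hours, a missing-sample case that the SAP's one-sample minimum does not clearly exclude. The peak rule gives no protection to the thrombin-generation and TEG/ROTEM draws.

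**What to change.** In SoA notes 18 and 19 and in Protocol 4.1.4 and 4.1.7.2, time the first post-dose sample from the actual end of the FIX product infusion. The protocol already anchors this way for the vector infusion, where note 8 sets a vital-sign reading at the end of infusion ± 2 minutes. With the draw tied to completion, the delivered share is 100% and this error is zero.

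Record the FIX infusion start and stop times and each draw time. For the FIX product, the visible text of Protocol 6.1.2 lists vials, volume and dosage, and SAP 7.2.1 lists product type and dose; neither mentions these times.

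In SAP 10.1, state that a draw made before the infusion ended is excluded from the peak. Without the timing change this only makes the handling consistent, as Step 3 of the working shows; for samples already drawn it is the only part that can still help, and only if the times were recorded.

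In the same edit, reconcile the unscheduled 30 (±2) minute sample in Protocol 9.3 with the 3-hour rule in SAP 4.3.5.

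The cost is wording and a few time fields. No sample is added, draws move by a few minutes at most, and no dose or infusion instruction changes.

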### 1.3. Schedule of Activities (SoA)

Tests and Assessments	Week -6 to -1 	Day 0 		Week 1 - 18 (±2 days)														Week 22 - 52 (±2 weeks)				Unscheduled Visits 					
	Screening	Pre-Vector Dosing	Vector Dosing	1	2	3	4	5	6	7	8	10	12	14	16	18	22	26	32	42	52 or End-of-Study						
Informed Consent 	X																										
Demographics, Medical, Surgical and Hemophilia History (including genotype and HLA) 	X																										
Physical Exam, Height, Weight  , and Vital Signs 	X	X 	X 		X		X		X		X		X		X		X	X	X	X		X 					
Liver ultrasound		X 																								X	
Target Joint Assessment 		X 																								X	
Laboratory																											
HBV, HCV, CD4, and HIV Serology Vaccination History 	X																										
α-fetoprotein	X																									X	
Standard Safety Panels 	X	X			X		X		X		X		X		X		X	X	X	X		X				X	
Lipid Panel and Urinalysis (dipstick)	X																									X	
LFT and Immunology Tests 	X	X			X 	X 	X 	X 	X 	X 	X 	X 	X 	X	X	X	X	X	X	X	X	X	X	X	X	X	X
Coagulation (aPTT, INR, and TAT) 		X																								X	
FIX Activity and Antigen 	X	X			X 	X 	X 	X 	X 	X 	X 	X 	X 	X	X	X	X	X	X	X	X	X	X	X	X	X	X
Bethesda Assay for FIX Inhibitor	X	X					X					X		X		X					X	X	X			X	
AAV Neutralizing Antibody	X	X			X	X		X						X												X	

Tests and Assessments	Week -6 to -1 	Day 0 	Week 1 - 18 (±2 days)												Week 22 - 52 (±2 weeks)				Unscheduled Visits 			
Genomic Banked Biospecimens Prep-D1	X 																					
Global Hemostasis Markers 		X																			X	
FIX Product Infusion 		X																				
FIX Incremental Recovery 		X																				
PF-06838435 Infusion 			X																			
Review Infusion Log	X	X	X	X	X	X	X	X	X	X	X	X	X	X	X	X	X	X	X	X	X	
Participant's QoL Assessment and Changes in Level of Activity Questionnaires 		X 						X						X					X			X
Health-economic Assessment		X						X						X					X			X

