#### 4.1.4. FIX Incremental Recovery

FIX incremental recovery will be measured up to 24 ( $\pm 1$ ) hours post-infusion of FIX protein products to assess time at maximum activity and percent recovery for exogenous FIX activity. The exogenous FIX activity levels will be determined by one-stage clotting assay. Participants are required to have at least 96 hours of washout for pd- or r-FIX or up to approximately 168 hours of washout for extended half-life rFIX prior to FIX incremental recovery test on Dosing Day (Day 0).

FIX incremental recovery assessments will be conducted by collecting blood samples at various time-points up to 24 ( $\pm 1$ ) hours from the start of FIX protein product infusion. Blood samples on Day 0 will be collected pre-infusion, 10 ( $\pm 2$ ) minutes, 1 hour  $\pm 10$  minutes, 3 hours  $\pm 10$  minutes, 6 hours  $\pm 10$  minutes, and 24 ( $\pm 1$ ) hours from the start-of-infusion of FIX protein product.

Samples for thrombin generation assessments will also be collected on Day 0 at pre-infusion and 10 ( $\pm 2$ ) minutes from the start-of-infusion of FIX protein infusion and evaluated by an

CCI performed at the central laboratory. For participants at selected sites depending on the testing capabilities, additional samples for global hemostasis may also be collected at pre-infusion and 10 ( $\pm$ 2) minutes from the start-of-infusion of FIX protein infusion and evaluated by the whole blood TEG and/or rotational thromboelastogram (ROTEM) locally.

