#### **4.1.6. Thrombotic Potential Assessments (ONLY for Participants Who Reach Vector-derived FIX:C Activity Levels >150% after the infusion of PF-06838435)**

Based on non-clinical studies in NHPs and the and the now closed Baxter study using hFIX-Padua, it is not predicted that vector-derived FIX:C activity levels >150% of normal will be achieved in this study. However, thrombin-antithrombin levels (TAT) as thrombotic potential will be measured if vector-derived FIX:C activity levels >150% of normal are achieved in any participant during the study. Blood samples for TAT on Day 0 (prior to FIX protein product infusion) will be used to establish baseline value.

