## **6.4. Study Intervention Compliance**

Deviation(s) from the prescribed dosage regimen should be recorded in the electronic case report form (eCRF).

Compliance with the infusion of FIX protein product and PF-06838435 on Day 0 is to be monitored and recorded by site staff.

After the infusion of FIX protein product on Day 0, participants will immediately be infused with PF-06838435. PF-06838435 will be infused via infusion pump and will be supervised by the investigational staff. The vial lot number, total volume, and infusion time are monitored and recorded by the site staff. Therefore, full compliance with PF-06838435 infusion is anticipated.

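### The SAP laboratory baseline rule can pick a Day 0 TEG/ROTEM or thrombin generation sample taken after FIX product, and SAP 9.2.2 and SoA footnote 19 misstate when hemostasis tests are collected

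*Protocol*

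**What the plan says.** **Order of events on Day 0.** Protocol 6.1.2: "On Day 0 participants will be infused with 100 IU/kg of their usual FIX protein product", over 10 (±2) minutes. SoA footnote 20: "After the completion of FIX protein product infusion, participants will receive PF-06838435 infused via infusion pump". Section 6.4: "After the infusion of FIX protein product on Day 0, participants will immediately be infused with PF-06838435". No interval in minutes is given.

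**Hemostasis samples.** Protocol 4.1.4: "Samples for thrombin generation assessments will also be collected on Day 0 at pre-infusion and 10" (±2) minutes from the start of the FIX product, with the assay "performed at the central laboratory". At selected sites, TEG and/or ROTEM may be drawn at the same two times and run locally. Footnote 19 gives the TEG/ROTEM times relative to the "start-of-infusion of FIX protein product on Day 0 and End-of-Study Visits".

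**Baseline.** SAP 9.2 uses the most recent evaluable laboratory value before PF-06838435 and does not define evaluable. SAP 9.2.2 plans change from baseline for the coagulation parameters and sets no baseline of its own. The protocol fixes a baseline for one test only, in Section 4.1.6: "Blood samples for TAT on Day 0 (prior to FIX protein product infusion) will be used to establish baseline value".

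**Who is tested.** The SoA row that begins "Coagulation (aPTT, INR, and TAT" has a Day 0 and an end-of-study entry and no FIX:C condition. Extra testing above 150% FIX:C is a separate row. SAP 9.2.2 instead says that INR, TAT, TEG and ROTEM are collected only in participants above 150%.

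**FIX product at Week 52.** The SoA infusion row, footnote 17 and Protocol 4.1.4, 4.1.7.2, 6.1.2 and 6.4 place the infusion on Day 0 only. SAP 7.2.1, Table 14.4.1.2 and Listing 16.2.5.1.2 still refer to FIX product at Week 52 or end of study.

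**The concern.** A change from baseline in hemostatic potential should compare the participant after the vector with the participant in washout. If baseline is instead a sample drawn minutes after a large dose of replacement factor, the change mixes loss of the infused product with gain from the vector. If some participants get the washout baseline and others the loaded one, a group summary mixes two different quantities.

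The protocol fixed this for TAT by naming the sample before FIX product. The SAP does not extend that rule to the other tests drawn around the same infusion.

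The two collection statements matter for conduct and programming. Footnote 19 asks a site to time an end-of-study draw from an infusion that is not scheduled, so the sample may be skipped or product given unnecessarily. The SAP 9.2.2 sentence could lead a programmer to treat scheduled INR and TAT results as out of scope.

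**Working it through.** The plan states no figure on this point, so there is none to reproduce. The check is one timing calculation and a comparison of texts.

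**1. Can the loaded sample be the last one before the vector?**

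Inputs: FIX infusion duration d = 10 ± 2, so 8 to 12 minutes (footnote 17, Section 6.1.2). Sample time s = 10 ± 2, so 8 to 12 minutes from the same start (footnote 19, Section 4.1.4). The vector starts at d + g, where the gap g ≥ 0 is not stated and is assumed here.

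The loaded sample is at or before vector start when s ≤ d + g. At nominal times, 10 ≤ 10 + g always holds. On an even grid of 0.1 minute there are 41 × 41 = 1,681 pairs (d, s):

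| Assumed gap g (min) | Pairs with s ≤ d + g | Share |
|---|---|---|
| 0 | 1,681 − 820 = 861 | 51% |
| 2 | 1,681 − 210 = 1,471 | 88% |
| 4 or more | 1,681 | 100% |

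These shares describe the allowed windows. They do not forecast how many participants are affected. The loaded sample can fall on either side of vector start, and with any appreciable gap it usually falls before.

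**2. How different is that sample?**

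The documents give no expected recovery. Assuming 0.5 to 1.5 IU/dL per IU/kg, the load is 100 × 0.5 = 50 to 100 × 1.5 = 150 IU/dL, on top of an endogenous level of at most 2 IU/dL. This is FIX activity only. Nothing in the documents converts it to TGA or TEG/ROTEM units.

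**3. Which tests are exposed?**

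| Test | Day 0 draw | Laboratory | Post-vector value visible in the text | Exposed? |
|---|---|---|---|---|
| TAT | Just before FIX product (footnote 15, Section 4.1.6) | Central | End of study; also above 150% | No |
| aPTT, INR | Day 0, order relative to FIX product not stated | aPTT local and central; INR central | End of study; also above 150% | Not settled |
| TGA | Before, and at 10 minutes | Central | Only through titles of SAP Tables 14.3.4.3.1 and 14.3.4.3.2 | Yes, where a post-vector value exists |
| TEG/ROTEM | Before, and at 10 minutes | Local, selected participants and sites | End of study (footnote 19) | Yes, mainly in listings, because SAP 9.2 builds tables from central results |

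**4. The 150% sentence in SAP 9.2.2.** It conflicts with the SoA coagulation row, which has no such condition. It conflicts with footnote 19, which limits TEG/ROTEM by participant and site. It conflicts with Section 4.1.6, because a Day 0 TAT baseline must be drawn before anyone's vector response is known. It also conflicts with the SAP's own tables: 14.3.4.3.1 covers the group above 150%, and 14.3.4.3.2 covers the same tests without that limit.

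**5. Footnote 19.** A 10-minute end-of-study draw needs an infusion start at end of study. No section schedules one.

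**The case against.** The strongest defence of the baseline rule is that SAP 9.2 requires an evaluable value, SAP Section 4 requires one usable for analysis, and SAP 9.2.2 ties the TEG/ROTEM draws to the recovery test. An analyst could treat the 10-minute sample as a recovery time point and pass over it. That is a sensible reading, but nothing in the SAP requires it. An undefined word does not reliably exclude the sample, so a wrong selection is possible rather than certain.

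Two stronger readings are tempting, and the documents do not support either.

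- A reader might infer that every participant's end-of-study TGA will be compared with a loaded baseline. No visible text schedules a routine end-of-study TGA draw. Sections 4.1.4 and 4.1.7.2 place TGA on Day 0. Footnote 19 has a redacted stretch before its timing sentence, so whether it covers TGA cannot be told. Table titles alone do not establish a sample.
- A reader might infer that a rise will be reported as a fall. Under an assumed recovery of 0.5, a participant going from 2 to 5 IU/dL changes by +3 from washout and by 5 − 52 = −47 from the loaded sample. One reaching 100 IU/dL still shows 100 − 52 = +48. Even in FIX activity the sign is not fixed, and SAP 9.2.2 does not tabulate FIX activity.

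On collection, the SoA governs what sites do, so the SAP sentence cancels no samples. Footnote 19 can also be read charitably as Day 0 times plus one product-free end-of-study sample. Both points stand and limit the harm, but the texts remain contradictory.

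**Conclusion.** The point holds, with minor impact. Followed literally, SAP 9.2 can select a sample carrying 100 IU/kg of FIX product as baseline for TEG/ROTEM and TGA, and the selection can differ between participants with infusion timing. That can distort change from baseline for TEG/ROTEM, and for TGA wherever a post-vector value exists. The size and sign in assay units cannot be derived from the documents, and the number of participants affected is unknown. TAT is already protected. The SAP 9.2.2 collection sentence is wrong, and footnote 19 cannot be carried out as written for the end-of-study 10-minute draw.

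The consequence is small. All analyses are descriptive, no stopping rule in Protocol 4.3.1 uses TEG/ROTEM or TGA, and the secondary endpoints are FIX activity and antigen. The closest link to a named endpoint is SAP 3.2.1, which lists thrombotic-potential laboratory parameters above 150% FIX:C as primary; Protocol 4.1.6 does not expect anyone to reach that level. The correction is still worth making because it costs almost nothing. The timing shares rest on an assumed gap and an even grid, and the FIX load rests on an assumed recovery.

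**What to change.** - **SAP 9.2.2, baseline:** for TEG/ROTEM and TGA, and for aPTT and INR where drawn on Day 0, define baseline as the last sample before the Day 0 FIX product infusion. This matches Protocol 4.1.6 for TAT.
- **SAP 9.2.2, collection:** limit the 150% sentence to the additional thrombotic-potential testing.
- **SoA footnote 19:** restrict the pre-infusion and 10-minute times to Day 0, and specify one end-of-study sample without FIX product.
- **SoA footnote 15:** state that aPTT and INR, like TAT, are drawn before FIX product.
- **SAP 7.2.1, Table 14.4.1.2 and Listing 16.2.5.1.2:** state that Week 52 FIX product is reported only for participants who actually received it.

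The cost is a minor protocol amendment covering two footnotes, with whatever ethics review Appendix 1 requires, and a few SAP sentences. No new visits, samples or tables are needed. The SAP changes fit before database lock, when Protocol 9.4 has the SAP finalized.
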